# 9.3. Other Efficacy Endpoints

Other efficacy endpoints (Non-primary or secondary endpoints) will be summarized on the ITT analysis set by visit for descriptive statistics only. No statistical treatment group comparison will be performed, unless otherwise specified.

# 9.3.1. Slit Lamp External Eye Exam and Biomicroscopy

The examination of anterior uveitis is performed on both eyes (study and non-study eye) by external examination and biomicroscopy using a slit lamp. Slit lamp examination will be completed at Day 1 (Screening), Day 4, Week 1, Week 2, Week 3 and Week 4.

Changes from baseline in signs and symptoms of anterior uveitis which include Anterior Chamber Cell Grade, Anterior Chamber Flare Grade, Limbal Injection, Hypopyon, Peripheral Anterior Synechiae, Posterior Synechiae, Keratic Precipitates and Eyelid are the interest of treatment efficacy.

Descriptive summaries of the observed exam results at each scheduled visit as well as the change from baseline at each post-baseline visit will be presented for both eyes (study and non-study eye), without imputation. The numerical value of the exam result categories will be used in the summaries. The higher score representing more severe symptoms.

Number and percentage of subjects with Eyelid categories of Normal or Abnormal as well as the categorical shift from baseline at each post-baseline visit will also be summarized. The percentages will be calculated based on the number of subjects at each visit in each treatment group of the ITT analysis set. The percentages on the shift will be calculated based on the number of subjects with both baseline and post-baseline values.

In addition to the descriptive summary, the change from baseline in anterior chamber cell grade and flare grade will be analyzed using Mixed effect Model Repeat Measurement (MMRM) method. The MMRM model will include the fixed categorical effects of treatment, random effect visit, and treatment-by-visit interaction, as well as continuous fixed covariates of baseline score. An unstructured covariance structure of random effect will be used for modeling the within-subject errors. If the unstructured covariance structure matrix results in a lack of convergence, the model will be fit using covariance matrices of the following order until convergence is met:

- Heterogeneous Toeplitz
- Heterogeneous First-order autoregressive
- Toeplitz
- First-order autoregressive

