#### 2.3.6. Sample Size and Power

Based on the Phase 2 clinical trial results, a true hazard rate of 0.2672 and 0.1098 is assumed for the time to treatment success in ADX-102 and vehicle group, respectively. With approximately 53% censoring rate, a sample size of 90 subjects (45 per group) yields 82% power to detect the superiority of ADX-102 over vehicle group with the use of a 2-sided log-rank test and a type I error of 0.05. Under the same assumption, a sample size of 120 subjects (60 per group) will provides 91% power.

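### SAP 9.3.1 makes visit a random effect in the MMRM and puts the unstructured matrix on it; visit should be fixed, with the matrix on the within-subject residuals

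*SAP*

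**What the plan says.** SAP 9.3.1 adds one inferential model to its descriptive summaries: "the change from baseline in anterior chamber cell grade and flare grade will be analyzed using Mixed effect Model Repeat Measurement (MMRM) method". Its terms are given as follows: "The MMRM model will include the fixed categorical effects of treatment, random effect visit, and treatment-by-visit interaction", together with baseline score as a continuous fixed covariate. On covariance it says: "An unstructured covariance structure of random effect will be used for modeling the within-subject errors".

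The fallback rule reads: "If the unstructured covariance structure matrix results in a lack of convergence, the model will be fit using covariance matrices of the following order". The order is heterogeneous Toeplitz, heterogeneous first-order autoregressive, Toeplitz, first-order autoregressive.

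The schedule is fixed in advance: "Slit lamp examination will be completed at Day 1 (Screening), Day 4, Week 1, Week 2, Week 3 and Week 4". That is one baseline and five post-baseline visits.

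The section does not say whether the random effect is by subject, whether a separate residual variance is kept, whether treatment-by-visit is fixed or random, or how standard errors and degrees of freedom are obtained.

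**The concern.** Visit is not a sample from a population of visits. Interest lies in the treatment difference at these five time points, which calls for a fixed categorical effect. The covariance sentence then merges two components that mixed-model software keeps apart: the matrix of a random effect (G-side) and the matrix of the within-subject errors (R-side).

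Three models fit the text:

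1. A subject-level random visit effect with an unstructured G matrix, plus a residual variance.
2. Visit and treatment-by-visit both random. An interaction containing a random factor is conventionally taken as random too.
3. The ordinary MMRM: visit fixed, unstructured R-side matrix. This is probably what was meant, but it contradicts the label on visit.

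The first carries a redundant parameter, which may produce a convergence or Hessian warning and so start the fallback list. The second has no fixed treatment contrast at each visit and judges treatment against variation over only five visits. A pre-specified analysis should not leave that choice to the programmer, particularly as SAP Section 2 places the analyses after database lock and unmasking.

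**Working it through.** **Plan's own figures.** The SAP gives none for this model. Its only power figures (SAP 2.3.6) concern the primary log-rank test. They reproduce with the Schoenfeld formula (42.3 events: 82.4% against 82%; 56.4 events: 91.6% against 91%) but do not enter this point. Only the 60 per group is used below.

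**Parameter count (model 1).** With T = 5 visits, an unstructured matrix has T(T+1)/2 = 5 × 6/2 = 15 parameters. A separate residual variance makes 16. The data supply 15 variances and covariances. The information matrix for V = G + σ²I has rank 15 with 16 parameters, so exactly one is redundant. With the R-side matrix alone it is 15 parameters, rank 15.

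**Does the redundancy reach the treatment effect?** Moving an amount c from G to the residual, (G − cI) + (σ² + c)I, leaves V unchanged. Assume SDs of 0.60, 0.75, 0.90, 1.00 and 1.05 over the five visits, 60 per arm and complete data. The Week 4 standard error is √(2 × 1.05²/60) = 0.1917 at every split tried. In a small REML simulation (62 trials, about 37% dropout by Week 4), the literal and R-side versions agreed to within 0.1% on the Week 4 standard error in 61. The exception was an optimiser failure of the over-parameterised version. The R-side fit converged in 62 of 62. That simulation serves only to compare the two versions: model standard errors were about 11% below the empirical SD in both (ratios 0.892 and 0.894), so it is no guide to calibration.

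**Mean structure.** If treatment-by-visit is fixed, treatment plus the interaction spans all 2 × 5 = 10 cell means. The rank is 10 with or without visit, so mislabelling visit costs nothing in the means. The means are affected only if the interaction is also random.

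**Fallbacks.** Each structure was fitted, in large samples, to three assumed true covariances with the SDs above:

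| Structure | Model SE / true SE, Day 4 | Model SE / true SE, Week 4 |
|---|---|---|
| Heterogeneous Toeplitz, heterogeneous AR(1) | 0.96-1.00 | 1.00-1.04 |
| Toeplitz, AR(1) | 1.44-1.46 | 0.82-0.83 |

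The reason is simple. An equal-variance structure uses roughly the average variance at every visit. Take variances rising in equal steps from 0.36 to 1.10 (0.36, 0.545, 0.73, 0.915, 1.10; mean 0.73):

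- Week 4: ratio √(0.73/1.10) = 0.815; rejection rate 2[1 − Φ(1.96 × 0.815)] = 11.0%.
- Day 4: ratio √(0.73/0.36) = 1.424; rejection rate 2[1 − Φ(1.96 × 1.424)] = 0.5%.

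The tabulated Week 4 ratios of 0.82-0.83 give 10.4-10.8% by the same formula. A simulation of 3000 null trials (60 per arm, variances from 0.36 to 1.10, correlation 0.6 per lag) gave 12.0% at Week 4 for AR(1) and 5.3% for the unstructured residual matrix.

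**The case against.** The strongest reply is that this is loose wording and nothing more. The covariance sentence says the matrix models within-subject errors, which is the R-side role, and the method is called MMRM. Read that way the model is the standard one and is identified. Even read literally, the treatment standard error does not change if the fit completes.

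Most of that stands, and it rules out several stronger readings that a reader might infer:

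- *The model is non-identifiable and so invalid.* This needs a subject-level random visit plus a separate residual variance, which the SAP never states. Even then the total covariance, and with it the treatment inference, is identified.
- *The analysis is likely to drop to a simpler structure.* The SAP uses a fallback only on non-convergence, and nothing in the documents makes that probable. A warning for the 16-parameter version is possible, no more.
- *The fallbacks give wrong standard errors.* The first two allow variances to differ by visit and were within about 4% of correct. AR(1) is reached only after the unstructured matrix and three other structures have failed.
- *This is the only model-based comparison of cell and flare grade.* SAP 9.2.1 to 9.2.3 plan Cox models and log-rank tests of time to cell grade reduction, flare success and flare grade reduction. The MMRM is the only model of mean change by visit.

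The reading with a random interaction also sits badly with the reference to within-subject errors, and nothing was computed for it. What the reply does not remove is that the text calls visit random, that no other section corrects it, and that it leaves the status of the interaction open.

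**Conclusion.** The specification is wrong as written and should be corrected, but the consequence is limited. On the literal reading there is one redundant covariance parameter (16 parameters, rank 15), no change to treatment estimates or standard errors if the fit completes, and some chance that a warning rather than the data selects the covariance structure. If the interaction is taken as random, the treatment contrast at each visit is lost as a fixed effect.

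The roughly 11-12% false-positive rate at Week 4, with about 0.5% at Day 4, belongs only to the equal-variance fallbacks and rests on assumed variances rising about threefold over the visits. The documents give no variances, correlations or dropout for these scores. With constant variance the cause of this distortion disappears.

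The model serves endpoints that SAP 9.3 places outside the primary and secondary set: "Other efficacy endpoints (Non-primary or secondary endpoints) will be summarized on the ITT analysis set by visit for descriptive statistics only", with the MMRM as a stated addition. No primary or secondary conclusion depends on it.

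**What to change.** Reword the model in SAP 9.3.1 along these lines: fixed effects of treatment, visit (categorical), treatment-by-visit and baseline score; no random effects; an unstructured within-subject residual (R-side) covariance over the five post-baseline visits. Keep the fallback list, but state that robust (sandwich) standard errors are used whenever a fallback structure is fitted.

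For flare, add the baseline ACC grade stratum as a fixed effect, since randomisation is stratified on it (SAP 2.3.5) and baseline flare does not carry it. Kenward-Roger degrees of freedom with the unstructured model are a reasonable option but are not needed to cure the error.

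The cost is a few words of SAP text. The one real drawback is that sandwich standard errors are slightly less stable at about 60 per arm, and this applies only if a fallback is reached.

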#### 9.3.2. Ocular VAS Scores

Ocular pain, blurred vision, photophobia and tearing will each be measured using a visual analogue scale. The VAS is a continuous 100 millimeter (mm) line and subjects will be asked to indicate their level of agreement to a statement (0 = no symptoms, 100 = worst possible symptoms) by placing a single vertical line on the scale. The VAS will be administered at Day 1 (Screening), Day 4, Week 1, Week 2, Week 3 and Week 4.

Descriptive summaries of the observed VAS scores at each scheduled visit as well as the change from baseline at each post-baseline visit will be presented without imputation. The higher score representing more severe symptoms.

#### 9.3.3. Best Corrected Visual Acuity

The BCVA is measured on both eyes (study and non-study eye) at Day 1 (Screening), Day 4, Week 1, Week 2, Week 3 and Week 4.

Descriptive summaries of the observed BCVA number of letters read at each scheduled visit as well as the change from baseline at each post-baseline visit will be presented for both eyes (study and non-study eye), without imputation. The higher number of letters read representing a better vision.

The number and percentage subjects with  $\geq 5$  letters change,  $\geq 10$  letters change, no change, or worsened from baseline will also be summarized. The percentages will be calculated based on the number of subjects with both baseline and post-baseline values in each treatment group of the ITT analysis set.

# 9.3.4. Visual Functioning Questionnaire – 25 (VFQ-25)

The VFQ-25 is a reliable and valid 25-item version of the 51-item National Eye Institute Visual Function Questionnaire (NEI-VFQ). The VFQ-25 will be self-administered at the beginning of the designated study visits, prior to any examinations (see Protocol Section 9.1.5 for exception). The VFQ-25 will be administered at Day 1 (Screening) and Week 4.

Scoring VFQ-25 with or without optional items is a two-step process:

First, original numeric values from the survey are re-coded following the scoring rules outlined in the "Version 2000, The National Eye Institute 25-Item, Visual Function Questionnaire" document (will refer it to as the Scoring Manual forward) Scoring Manual **Table 2**. All items are scored so that a high score represents better functioning. Each item is then converted to a 0 to 100 scale so that the lowest and highest possible scores are set at 0 and 100 points, respectively. In this format scores represent the achieved percentage of the total possible score, e.g. a score of 50 represents 50% of the highest possible score.

In step 2, items within each sub-scale are averaged together to create the 12 sub-scale scores. The 12 sub-scales are: General Health, General Vision, Ocular Pain, Near Activities, Distance Activities, Vision Specific Social Functioning, Vision Specific Mental Health, Vision Specific Role Difficulties, Vision Specific Dependency, Driving, Color Vision and Peripheral Vision. Scoring Manual **Table 3** indicates the items contribute to each specific sub-scale. Items that are left blank (missing data) are not taken into account when calculating the scale scores. Sub-scales with at least one item answered can be used to generate a sub-scale score. Hence, scores represent the average for all items in the subscale that the respondent answered.

#### Sub-scale Scoring Formula:

Mean = Sum of (Score for each item with a non-missing answer) / Total number of items with non-missing answers

Note: 100 = Best, 0 = Worst possible score.

# Composite Score Calculation:

To calculate an overall composite score for the VFQ-25, simply average the vision-targeted subscale scores, excluding the general health rating question. By averaging the sub-scale scores rather than the individual items we have given equal weight to each sub-scale, whereas averaging the items would give more weight to scales with more items.

Descriptive summaries of the observed VFQ-25 scores at each scheduled visit as well as the change from baseline at each post-baseline visit will be presented without imputation. The higher score representing better functioning. Both individual sub-scale score and the overall composite score of VFQ-25 will be summarized. Unscheduled and early termination visits will not be assigned to an unplanned study visit using the analysis windows described in SAP Section 3.2.9 (Table 3). Early termination visit will be summarized separately from the Week 4 summary. Unscheduled visit will not be summarized but will be listed.

In addition to the descriptive summary, the change from baseline at Week 4 in the overall composite score will be analyzed using the two-sample t-test with two-sided type 1 errors of 0.05.

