- Ocular scores and VFQ-25 self-administered survey (version 2000) will be completed prior to any other study procedures at that visit. The only exception is for the VFQ-25 when a subject is being seen for a routine study visit that becomes an ET visit because the subject receives rescue therapy. In these cases, the VFQ-25 must still be administered but it may be after other examinations.
- Ocular pain, lacrimation, photophobia, and blurry vision will be measured by the subject completing a Visual Analog Scale (VAS).
- During Screening only, the following 3 uveitis-specific diagnostic tests will be obtained in all subjects experiencing their first episode of anterior uveitis, or in subjects experiencing a repeat episode where prior tests of this nature have not been previously performed:
  - 1) HLA-B27 (Human leukocyte antigen subtypes B\*2701-2759)
  - 2) Chest X-ray
  - 3) Treponemal antibody test(s) including one or more of the following:
    - a. FTA-ABS (Fluorescent treponemal antibody absorption)
    - b. TP-PA (T. pallidum particle agglutination assay)
    - c. MHA-TP (Micro-hemagglutination assay)
    - d. Laboratory specific automated Immunoassay (IA)

A non-treponemal antibody test such as RPR (Rapid Plasma Reagin) alone is not sufficient. If the study subject was tested prior to the screening visit, there needs to be evidence that these tests were performed:

- 1) HLA-B27 at any time in the past
- 2) Chest X-ray within the previous 6 months unless new onset pulmonary symptoms are documented
- Treponemal antibody test(s) within the previous 6 months unless intervening new onset symptoms of any STD, or STD exposure are documented

Additional testing such as for RPR, ACE, ANCA, quantiferon and ANA may be performed at the discretion of the investigator.

- Safety laboratory tests are hematology including: "hemoglobin, hematocrit, red blood cell (RBC) count, RBC morphology, white blood cell (WBC) count with differential, mean corpuscular volume (MCV), mean corpuscular hemoglobin (MCH), mean corpuscular hemoglobin concentration (MCHC), and absolute platelet count" and chemistry including: "albumin, alkaline phosphatase, alanine aminotransferase (ALT; SGPT), aspartate aminotransferase (AST; SGOT), bilirubin (total and direct), blood urea nitrogen (BUN), calcium, carbon dioxide (CO2), chloride, creatinine, creatinine phosphokinase (CPK), glucose, phosphate, potassium, sodium, total protein, and uric acid."

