# 2.3.4.3. Rescue Therapy

Rescue therapy will be administered after completion of the Week 1 or Week 2 assessments if any one of the below criteria are met:

- Worsening of visual acuity due, in the opinion of the Investigator, to non-infectious anterior uveitis by  $\geq 2$  lines or  $\geq 10$  letters using ETDRS testing from **Day 1** to **Week 1** or any time after **Week 1** (compared to Day 1)
- Subject demonstrates one unit or more increase in ACC grade from **Day 1** to **Week 1** or any time after **Week 1** (compared to Day 1)
- Subject fails to show improvement in ACC grade from Day 1 to Week 2

The protocol recommended rescue therapy is Durezol® (difluprednate ophthalmic emulsion 0.05%) four times a day (QID) plus Cyclogyl (cyclopentolate hydrochloride ophthalmic solution, 1%) up to QID, as needed (PRN). Durezol® tapered to three times a day (TID), twice a day (BID), once a day (QD) each subsequent week if ocular exam and symptoms improve. Alternative rescue therapy may be given at the discretion of the Investigator.

Once it is determined that rescue therapy is needed, the subject should be considered an Early Termination and the Week 4 (Visit 6) assessments should be completed.

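### The Week 4 VFQ-25 test leaves out everyone who exits before Week 4, including all subjects rescued by then, although a questionnaire is collected at their exit

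*SAP*

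**What the plan says.** SAP 9.3.4, under the composite score calculation, says that "the change from baseline at Week 4 in the overall composite score will be analyzed using the two-sample t-test", at a two-sided 0.05 level. The same subsection sets three rules for the data:

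- On windowing: "Unscheduled and early termination visits will not be assigned to an unplanned study visit using the analysis windows".
- On early termination (ET) data: "Early termination visit will be summarized separately from the Week 4 summary".
- On missing data, for the descriptive summaries: "change from baseline at each post-baseline visit will be presented without imputation". No imputation is named for the t-test either. The LOCF rule in SAP 3.2.5 covers the primary and the listed secondary endpoints, and VFQ-25 is not among them.

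SAP 2.3.4.3 fixes the status of rescued subjects: "Once it is determined that rescue therapy is needed, the subject should be considered an Early Termination". The Week 4 assessments are then done at that visit. Protocol 5.4.4 lists the VFQ-25 among the Visit 6/EOT/ET procedures. The footnote to Table 2 in SAP 2.3.3 covers a routine visit that turns into an ET visit because of rescue: "In these cases, the VFQ-25 must still be administered but it may be after other examinations".

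SAP 2.2.1.2 lists Time to Rescue as a secondary efficacy endpoint. SAP 2.2.1.3 places VFQ-25 among the other efficacy endpoints, and SAP 9.3 puts those on the ITT set.

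**The concern.** A subject rescued before Week 4 has one post-baseline VFQ-25, taken at exit. The only later contact is the Week 5 telephone call, which covers adverse events and medications. Because the t-test uses Week 4 values only, this subject contributes nothing to it. The two groups tested are selected on an outcome that treatment may affect, so randomization no longer protects the comparison, even though SAP 9.3 assigns the endpoint to the ITT set.

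The SAP handles treatment failure differently elsewhere. In the primary analysis (SAP 9.1, Table 4) a rescued subject is censored at Week 4 and so stays at risk as a non-success. The responder endpoint in SAP 9.2.5 counts grade 0 only without rescue. The repeated-measures model for cell and flare grade in SAP 9.3.1 can use a rescued subject's visits up to exit. VFQ-25 has a single post-baseline time point, so nothing comparable happens there.

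At stake is how this one test is read. A null result could reflect loss of the failures rather than lack of effect, and a positive result would apply only to subjects who stayed to Week 4 without rescue.

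**Working it through.** **The plan's own figure.** The documents give no sample size, SD or effect for VFQ-25. The only power statement is for the primary log-rank test (SAP 2.3.6), and it reproduces. The hazard ratio is 0.2672/0.1098 = 2.434, with logarithm 0.889. With 53% censored, events are 0.47 × 90 = 42.3 and 0.47 × 120 = 56.4. By Schoenfeld's formula, power = Φ(√(events/4) × 0.889 − 1.96). This gives 82.4% and 91.6%, against the stated 82% and 91%. The VFQ-25 point does not touch these figures.

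**Who is in the t-test.**

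1. Rescue makes the subject an ET (SAP 2.3.4.3). Under the criteria there, this can happen from Week 1 onward.
2. In SAP 3.2.9, Table 3, Days 6–11 are Week 1, Days 12–18 are Week 2, and only Day 25 onward is Week 4. A Week 1 or Week 2 exit score would miss Week 4 even under default windowing. For these subjects the exclusion comes from testing a Week 4 change with no imputation. The no-windowing sentence in 9.3.4 matters only for late ET visits, Day 25 onward.
3. Early exits for reasons other than rescue are excluded in the same way.

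**How many.** Under the planning assumption, 0.53 × 120 ≈ 64 subjects are without treatment success. Rescued subjects are an unstated part of these, so the planning figures allow anything from 0 to about 64.

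**What the exclusion does.** Let r be the fraction rescued before Week 4 and g the gap in mean change between non-rescued and rescued subjects, with A for ADX-102 and V for vehicle. Ignoring other early exits:

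all-subject difference − completer difference = r_V × g_V − r_A × g_A

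**Illustration.** Assumptions, none from the documents: 60 per arm, SD 1 within rescued and non-rescued subjects, the same gap in both arms, and a drug effect on VFQ-25 only through preventing rescue. The completer difference is then 0 by construction.

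| Rescue A / V | In t-test | Detectable at 80% power | All-subject difference, gap 0.5 to 1.0 SD |
|---|---|---|---|
| 10% / 20% | 54 v 48 | 0.56 SD | 0.05 to 0.10 SD |
| 20% / 40% | 48 v 36 | 0.62 SD | 0.10 to 0.20 SD |
| 20% / 50% | 48 v 30 | 0.65 SD | 0.15 to 0.30 SD |

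The third column is 2.80 × √(1/n_A + 1/n_V). With 60 v 60 it is 0.51 SD, but mixing rescued and non-rescued subjects widens the spread. At 20%/40% with a gap of 1 SD, the standard error of the all-subject comparison is √((1.16 + 1.24)/60) = 0.20, so its detectable difference is 2.80 × 0.20 = 0.56 SD. Its power for the 0.20 SD difference is about 17%, and at 20%/50% for 0.30 SD about 32%.

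**Sensitivity to the equal-gap assumption.** On an assumed scale with SD 15, let non-rescued subjects gain 18 points on drug and 15 on vehicle, rescued subjects gain 0, and rescue be 20%/40%. Completers differ by 18 − 15 = 3.0 and all subjects by 0.8 × 18 − 0.6 × 15 = 5.4. At the same rescue rates the sign reverses if g_A is more than twice g_V.

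**The case against.** The strongest reply is that this is one exploratory test. SAP 3.2.3 bases inference on a single primary endpoint, and rescue is captured both there and in Time to Rescue. Keeping ET data apart also looks deliberate: SAP 10.3 does the same for laboratory and vital-sign data, which are likewise taken only at Visits 1 and 6. All of this stands and limits the weight of the point. It does not make the Week 4 test a comparison of the randomized groups.

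The remedy has drawbacks too. It pools scores from around Day 8 or Day 15 with scores from Day 29, and the mix may differ by arm. Some ET questionnaires follow other examinations, and a dilated fundus exam is scheduled at every clinic visit (Protocol 9.1.10). These are reasons to report both analyses, not to leave the selection unstated. Protocol 9.1.5 on the VFQ-25 is not in the public text, so any intended use of ET scores described there cannot be checked.

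A reader might infer more than the documents support:

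- *Every rescued subject is lost, or the ET scores are discarded.* A subject who first needs rescue at the scheduled Week 4 visit keeps a Week 4 value, and ET scores get their own descriptive summary.
- *The test is biased toward no difference.* The zero completer difference above follows from the assumed inputs. The documents do not settle the sign.
- *The VAS summaries share the fault.* SAP 9.3.2 is descriptive only: "Descriptive summaries of the observed VAS scores at each scheduled visit as well as the change from baseline at each post-baseline visit will be presented". It has no ET exclusion, so the default windowing in SAP 9 places an ET score at the visit window in which it occurred.

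**Conclusion.** The exclusion is certain on the text: no subject who leaves before Week 4 enters the t-test, and a score is collected from those who complete the exit visit. The consequence is uncertain. Under the illustrative rescue rates, 18 to 42 of 120 subjects drop out of the test (120 − 102 and 120 − 78), and the completer and all-subject differences diverge by 0.05 to 0.30 SD. These figures rest on assumed rescue rates, an assumed common gap, and no other early exits. An ET-inclusive comparison would still have low power for differences of that size, so its value lies in what is being compared rather than in sensitivity. The point warrants a cheap improvement to an exploratory analysis. It has no bearing on the primary endpoint, its power or the secondary endpoints.

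**What to change.** In SAP 9.3.4, before unmasking:

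- Add a between-arm comparison, in the ITT set, of change in the composite from baseline to the Visit 6/EOT/ET questionnaire. Use the Week 4 score for subjects who reach Week 4 and the ET score for those who exit earlier.
- Keep the Week 4 t-test, report it beside the new comparison, and label it as a completer comparison.
- Report by arm the number of subjects in each analysis, the number with no post-baseline VFQ-25, and the study day of the ET questionnaires.
- State the two limitations: assessment time differs between subjects and possibly between arms, and some ET questionnaires follow other examinations.

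Restoring default windowing would not be enough, because a Week 1 or Week 2 exit maps to those weeks; the tested change itself has to be redefined. The cost is a paragraph of SAP text and one derived variable. No new data, visits or subject burden are needed. The added test would be exploratory, like the existing one, and SAP 3.2.3 plans no multiplicity adjustment.

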# 2.2.1.3. Other Study Efficacy Endpoints

- Change in signs and symptoms of anterior uveitis which include Anterior Chamber Cell Grade, Anterior Chamber Flare Grade, Limbal Injection, Hypopyon, Peripheral Anterior Synechiae, Posterior Synechiae and Keratic Precipitates by Slit Lamp Exam
- Change in Ocular Pain, Lacrimation, Photophobia and Blurry Vision by Visual Analogue Scale (VAS).
- Change in Best Corrected Visual Acuity (BCVA)
- Change in Visual Functioning Questionnaire 25 (VFQ-25) Scores

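### The Week 4 VFQ-25 test leaves out subjects rescued before Week 4, and its change-score t-test is usually less precise than an ANCOVA on data already collected

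*SAP*

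**What the plan says.** SAP 2.2.1.3 lists "Change in Visual Functioning Questionnaire 25 (VFQ-25) Scores" among the other efficacy endpoints. The default for that tier in SAP 9.3 is descriptive: "No statistical treatment group comparison will be performed, unless otherwise specified". Section 9.3.4 does specify a comparison: "the change from baseline at Week 4 in the overall composite score will be analyzed using the two-sample t-test", two-sided at 0.05. It names no baseline covariate and no stratum.

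The questionnaire is scheduled at Day 1 and Week 4 only. Under SAP 2.3.4.3, once rescue is needed, "the subject should be considered an Early Termination and the Week 4 (Visit 6) assessments should be completed". The notes to SAP Table 2 confirm that a score is due at a visit that turns into a rescue visit: "the VFQ-25 must still be administered but it may be after other examinations".

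For VFQ-25, SAP 9.3.4 does not assign early-termination visits to the analysis windows and does not impute. It adds: "Early termination visit will be summarized separately from the Week 4 summary". LOCF in SAP 3.2.5 covers only the primary and key secondary endpoints.

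**The concern.** Section 9 of the SAP places all efficacy analyses on the ITT set, but this test can use only subjects with a Week 4 value. Those rescued or discontinued earlier drop out, and their scores appear only in a separate descriptive summary.

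Rescue is triggered by response: loss of visual acuity, a rise in ACC grade, or "Subject fails to show improvement in ACC grade from Day 1 to Week 2". Selection into the test is therefore post-randomisation and related to outcome. If vehicle subjects are rescued more often and rescued subjects score worse, the vehicle arm loses its worst scores and a real benefit is understated. The study report would then carry a p-value on patient-reported visual function that readers may take for an ITT result.

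A second, smaller point is precision. A change score subtracts the whole baseline value whatever its correlation with Week 4, whereas ANCOVA estimates how much to subtract. The SAP already adjusts for baseline among its other endpoints: the cell and flare grade MMRM in 9.3.1 includes "continuous fixed covariates of baseline score".

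**Working it through.** **The plan's own figures.** None is given for this test. The only power figures (SAP 2.3.6) concern the primary log-rank test and are unaffected. With a hazard ratio of 0.2672/0.1098 = 2.434 and 47% of subjects having events, Schoenfeld's formula gives 82.4% at 90 subjects and 91.6% at 120, against the stated 82% and 91%.

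**Who is in the test.**
1. Rescue can follow the Week 1 or Week 2 assessments and makes that visit an early termination.
2. The subject's only post-baseline VFQ-25 is then the early-termination score.
3. That score is not windowed to Week 4 and nothing is imputed.
4. General windowing would not change this for Week 1 or Week 2 rescues, because the Week 4 window in SAP 3.2.9 opens at Day 25. LOCF would have only the baseline score to carry from the schedule.
5. The same holds for other discontinuations before Week 4. A subject who first meets rescue criteria at the scheduled Week 4 visit may still have a Week 4 value; the SAP does not say.

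**Size of the selection effect (all inputs assumed).** In each arm let p be the share rescued before Week 4 and d the shortfall in their mean change against the non-rescued, on whichever score is taken to represent them. Then

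all-subject mean change = non-rescued mean − p·d,

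so the completer difference (ADX-102 minus vehicle) understates the all-subject difference by p_V·d_V − p_A·d_A. With equal d in both arms this is the gap in rescue rates times d, in points on the 0–100 composite:

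| Rescue gap (vehicle − ADX-102) | d = 5 | d = 10 | d = 15 |
|---|---|---|---|
| 0 | 0 | 0 | 0 |
| 0.10 | 0.5 | 1.0 | 1.5 |
| 0.20 | 1.0 | 2.0 | 3.0 |
| 0.30 | 1.5 | 3.0 | 4.5 |

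It can reverse. With 30% rescued in both arms and deficits of 5 (vehicle) and 10 (ADX-102), 0.3×5 − 0.3×10 = −1.5, an overstatement of 1.5 points.

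**Precision.** Let r be the baseline-to-Week-4 correlation, with equal variance σ² at both visits (assumed). Per subject, the change score has variance 2σ²(1 − r) and the ANCOVA residual has σ²(1 − r²). The ratio is (1 − r²)/(2(1 − r)) = (1 + r)/2, and the standard error falls by 1 − √((1 + r)/2). The simulated columns use 20,000 runs per cell with baseline and two ACC-grade terms in the model, and grades assumed at 50/35/15% with no effect on the score.

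| r | Variance ratio (1 + r)/2 | SE reduction | Simulated ratio, 60 per arm | Simulated ratio, 40 per arm |
|---|---|---|---|---|
| 0.3 | 0.65 | 19.4% | 0.67 | 0.68 |
| 0.5 | 0.75 | 13.4% | 0.76 | 0.78 |
| 0.7 | 0.85 | 7.8% | 0.87 | 0.88 |
| 0.9 | 0.95 | 2.5% | 0.98 | 0.99 |

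With unequal SDs (Week 4 to baseline ratio 0.6 to 1.5, r of 0.5 or 0.7), the large-sample ratio runs from 0.35 to 0.998 and is never above 1.

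**The case against.** - **Nothing depends on it.** SAP 3.2.3 rests inference on the single primary endpoint. This stands and limits the importance of the point.
- **The t-test is valid and ANCOVA is a preference.** The t-test is indeed valid among the subjects it includes, and the gain is negligible at r = 0.9. But the baseline score is already collected and adjustment costs nothing.
- **The missing ACC stratum breaks no rule.** Correct. The SAP stratifies time-to-event and categorical analyses, and the cell and flare MMRM has no ACC-stratum term. The case for ACC grade is that it was a randomisation stratum.
- **Keeping early-termination scores apart is deliberate and defensible.** They may date from Week 1 or 2 and may follow other examinations. This is a good reason not to merge them into the main Week 4 result. It is not a reason to have no analysis that includes these subjects.
- **The windowing and imputation sentences are in the descriptive paragraph.** True, but the t-test sentence that follows gives no other data rule.
- **Exclusions are partly reported already.** SAP 6.1 and 8.2 give discontinuation and rescue counts and reasons by arm. Only a table specific to this test would be new.
- **The SAP is unclear on whether this test should exist.** Section 9 rules out comparisons for endpoints below secondary, without the exception that 9.3 allows. This stands and should be reconciled.

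**Conclusion.** The concern holds, at a low level of importance. As written, the VFQ-25 test is a completer comparison whose membership depends on response. The size and direction of any bias cannot be derived from the documents. Over the assumed ranges above it runs from 4.5 points understated, through zero, to 1.5 points overstated; understatement is the likelier direction if rescue is commoner on vehicle. These figures cover rescue only, not other early terminations. The precision loss is real but depends on the unknown correlation: the t-test's standard error would be cut by about 19% at r = 0.3 and 2.5% at r = 0.9, before the small cost of the extra model terms. The primary and secondary analyses are untouched.

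**What to change.** 1. Replace the t-test in SAP 9.3.4 with an ANCOVA on the Week 4 composite score, with treatment, baseline composite score and randomised baseline ACC grade. State whether a subject who first meets rescue criteria at the scheduled Week 4 visit contributes that visit's score.
2. Prespecify a sensitivity ANCOVA on all ITT subjects with a post-baseline VFQ-25, using the early-termination score for those rescued or discontinued before Week 4. ANCOVA alone does not cure the selection. Read the two results side by side; the sensitivity result does not replace the Week 4 result.
3. Report the number excluded from the Week 4 test by arm and reason.
4. Align the general sentence in SAP 9 with the exception in 9.3, so that it is clear the comparison is intended.

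The cost is SAP wording; no new data are needed. The sensitivity analysis has its own weakness. Early-termination scores are taken sooner and may follow other examinations, which could favour the arm with less rescue. If scores would improve by 2, 5 or 10 points between that visit and Week 4 (assumed), a 0.20 gap in rescue rates shifts the result by 0.2×2 = 0.4, 0.2×5 = 1.0 or 0.2×10 = 2.0 points. Subjects lost without an early-termination visit, whom Protocol 6.4 anticipates, remain missing from both analyses and should be counted.
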